## **6.7 BASELINE, TIME WINDOWS AND CALCULATED VISITS**

Where a baseline value is required, this will be defined as the last non-missing value prior to first administration of afatinib.

The time windows for subsequent clinic visits is 28 -7/+2 days. The end of treatment (EoT) visit can be anything up to a maximum of 14 days after the last trial drug intake and the follow-up visit should be between 28 and 35 days after the EoT visit.

Nominal visit numbers as recorded in the eCRF will be used where required and there will be no windowing.

Study day will be calculated relative to the date of the first administration of study drug. The day prior to first administration of study drug will be 'Day -1' and the day of first administration of study drug will be 'Day 1'; therefore 'Day 0' will not exist.

## **7. PLANNED ANALYSIS**

Unless otherwise stated, for end-of-text tables, the set of summary statistics is: N / Mean / SD / Min / Median / Max.

For tables that are provided for endpoints with some extreme data, median, quartiles and percentiles should be preferred to mean, standard deviation, minimum and maximum.

Tabulations of frequencies for categorical data will include all possible categories and will display the number of observations in a category as well as the percentage (%) relative to the respective treatment group, unless otherwise stated. Percentages will be rounded to one decimal place. The category missing will be displayed only if there are actually missing values.

### **7.1 DEMOGRAPHIC AND OTHER BASELINE CHARACTERISTICS**

Only descriptive statistics are planned for this section of the report. Demographic and baseline characteristic parameters collected and to be presented include

- Age [years]
- Age class (*<65, ≥65 years and <75, ≥75 years*)
- Gender (*Male, Female*)
- Race and ethnicity (as defined in the eCRF)
- Country
- Height [cm]
- Weight [kg]
- Body mass index [ $\text{kg}/\text{m}^2$ ] (defined as  $\text{weight} [\text{kg}]/(\text{height} [\text{cm}]/100)^2$ )
- Body surface area [ $\text{m}^2$ ] (defined as:  $0.007184 * (\text{height}^{0.725}) * (\text{weight}^{0.425})$ )
- Smoking status (*Never-smoked, Ex-smoker, Current smoker*)
- Smoking history [pack-years]
- Baseline ECOG score
- EGFR mutation type (*common, uncommon only*)
- Oncology history
- Previous therapies:
  - Systemic chemotherapies
  - Other anti-cancer therapies
  - Radiotherapies
- Previous surgeries for trial disease

This section will include a summary of all the subgroup variables detailed in [Section 6.4](#).

### **7.2 CONCOMITANT DISEASES AND MEDICATION**

Only descriptive statistics are planned for this section of the report. Only concomitant therapies for rash and diarrhoea were collected on the CRF and will be summarised.

For baseline conditions and signs and symptoms of the trial disease also only descriptive statistics will be presented.

### **7.3 TREATMENT COMPLIANCE**

There is no analysis planned for treatment compliance.

### **7.4 PRIMARY ENDPOINT**

Refer to [Section 7.8](#).

### **7.5 SECONDARY ENDPOINTS**

#### **7.5.1 Key secondary endpoint**

This section is not applicable as no key secondary endpoints have been specified in the protocol.

#### **7.5.2 Secondary endpoints**

The secondary endpoints will be analysed as described below:

##### **Number of patients with drug related adverse events**

Refer to [Section 7.8](#).

##### **Time to symptomatic progression (TTSP)**

Defined as the time (number of days) from first administration of afatinib to the date of first documented clinically significant symptomatic progression that required stopping afatinib according to investigator's assessment.

Patients will be considered to have clinically significant symptomatic progression if the reason for termination of trial medication is recorded as 'progressive disease' or 'worsening or AE of underlying cancer disease', on the termination of trial medication eCRF page.

Therefore TTSP will be derived as:

$TTSP \text{ [days]} = \text{date of last administration of trial drug (where 'progressive disease' or 'worsening or AE of underlying cancer disease' selected on the termination of trial drug eCRF page)} - (\text{date of start of treatment}) + 1$

Kaplan-Meier estimates and 95% confidence intervals for the 25th, median, and 75th percentiles of the survival distribution will be calculated for TTSP. Greenwood's standard error estimate will be used. Kaplan-Meier curves will also be produced.

##### *Censoring rules for TTSP:*

- For patients who have 'other AE', 'non-compliance with protocol', 'lost to follow-up', 'patient refusal to continue taking trial medication' or 'other' recorded on the termination of trial medication eCRF page, these patients will be censored at the date of last administration of the trial drug recorded on the termination of trial drug page;
- For patients who are still on treatment, these patients will be censored at cut-off date for interim analysis and at the date of EOT visit for final analysis.

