The sponsor may remove patients from the study after completion of the primary analysis if the patient has access to afatinib through marketed product, an expanded-access program, named patient use program, or compassionate use protocol or other means based on local regulation. The cost of any ongoing supply of afatinib will be incurred by the sponsor. If a patient is removed from the study treatment, an end of treatment and follow-up visit will be performed to ensure all adverse events are reported and followed up.

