6.1.4 End of Treatment (EOT) visit

All patients should be evaluated at the end of their trial treatment. This visit should be completed on the day of the patient's last dose on trial medication or up to 14 days later.

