7.3.2 Secondary analyses

TTSP

TTSP is the time from the date of the first administration of afatinib to the date of first documented clinically significant symptomatic progression that requires stopping afatinib according to investigator's assessment.

TTSP [days] = date of last administration of trial drug - (date of start of treatment) + 1

Kaplan-Meier estimates and 95% confidence intervals for the 25th, median, and 75th percentiles of the survival distribution will be calculated for TTSP, using Greenwood's standard error estimate. Kaplan-Meier curves will be produced without confidence intervals.

Proprietary confidential information.

© 2019 Boehringer Ingelheim International GmbH or one or more of its affiliated companies. All rights reserved.

This document may not - in full or in part - be passed on, reproduced, published or otherwise used without prior written permission.

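### Final-analysis TTSP censoring at the EOT visit adds up to 14 off-drug days for patients 'still on treatment', while events and all other censorings are dated at the last dose

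*SAP*

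**What the plan says.** In SAP 7.5.2 an event is the "date of first documented clinically significant symptomatic progression that required stopping afatinib", identified from the reason given on the termination page. Its date is the last dose. Protocol 7.3.2 gives the same derivation: "TTSP [days] = date of last administration of trial drug - (date of start of treatment) + 1".

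There are two censoring rules in SAP 7.5.2:

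- Patients who stopped for a listed reason other than progression, including 'other': "these patients will be censored at the date of last administration of the trial drug recorded on the termination of trial drug page".
- Patients still on treatment: "these patients will be censored at cut-off date for interim analysis and at the date of EOT visit for final analysis".

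On the timing of the EOT visit, Protocol 6.1.4 says "This visit should be completed on the day of the patient's last dose on trial medication or up to 14 days later", and SAP 6.7 gives the same 14-day maximum. Protocol 3.3.4.1 adds a route by which a patient can leave while still benefiting: "The sponsor may remove patients from the study after completion of the primary analysis", if afatinib is available by other means. An EOT visit is then required.

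**The concern.** Two things look wrong in the final analysis.

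1. **Different clocks.** Events and the first group of censorings stop at the last dose. The second group stops at a visit that may be two weeks later. Follow-up is lengthened only for patients without an event.
2. **An ill-defined group.** The EOT visit marks the end of treatment (Protocol 6.2.3), so a patient who has one is not still on treatment, and a patient who is still on treatment has none. A patient removed by the sponsor has an EOT visit. If that patient's reason is recorded as 'other', both rules apply and the SAP gives no order of precedence. Two programmers could derive different times from the same record.

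At stake is the accuracy and reproducibility of a secondary, descriptive efficacy result. No hypothesis test depends on TTSP.

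**Working it through.** The plan states no TTSP estimate or event count, so there is no figure to reproduce.

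**Step 1: size of the mismatch per patient.** Let S be the first dose, L the last dose and V the EOT visit.

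- Event: L − S + 1 (Protocol 7.3.2, SAP 7.5.2)
- Censored, stopped for another reason: L − S + 1
- Censored, 'still on treatment', final analysis: V − S + 1

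The excess is V − L. By Protocol 6.1.4 and SAP 6.7 it lies between 0 and 14 days (14 / 30.4375 = 0.46 month).

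**Step 2: direction.** An event is a stop of afatinib dated at L, so no patient can have an event between L and V. The Kaplan-Meier estimate is the product of (1 − d/n) over event times. Moving a censoring time from L to V can only raise n at other patients' event times in that interval and leaves every d unchanged. Each factor is therefore the same or larger, and the curve moves up or stays put.

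**Step 3: effect on the quartiles.** This needs assumptions that the documents do not supply:

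- exponential TTSP with a median of 11 months (the PFS median of the afatinib arm of trial 1200.34 in Protocol 2.3, a proxy only) or 15 months (assumed);
- 500 patients (Protocol 3.3), with uniform accrual over 24 or 36 months (assumed);
- 3 to 24 months of follow-up after the last entry (assumed);
- stopping for other reasons at one quarter of the event hazard, which is 20% of stops (assumed).

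There were 400 simulated trials per row. Shifts are in days against last-dose censoring, given as gap uniform on 0–14 days / every gap 14 days.

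| Median (months) | Accrual + follow-up (months) | Still on treatment | Shift in median | Shift in 75th percentile |
|---|---|---|---|---|
| 11 | 36 + 24 | 5% | 0 / 0 | 0 / 0 |
| 11 | 36 + 12 | 13% | 0 / 0 | 2.0 / 3.8 |
| 11 | 36 + 6 | 21% | 1.0 / 1.9 | 4.1 / 8.6 |
| 11 | 24 + 3 | 35% | 2.8 / 5.9 | 10.0 / 20.1 |
| 15 | 36 + 24 | 11% | 0 / 0 | 1.6 / 2.7 |
| 15 | 36 + 12 | 21% | 0.7 / 1.2 | 5.4 / 10.9 |
| 15 | 36 + 6 | 30% | 2.0 / 4.2 | 7.7 / 14.8 |
| 15 | 24 + 3 | 45% | 5.0 / 10.4 | not reliable |

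In the last row the true 75th percentile is 2 × 15 = 30 months and the longest possible follow-up is 24 + 3 = 27 months, so it is often not reached. A repeat simulation put the largest median shift at about 9 days rather than 10.4. The largest relative shift is 10.4 / 457 = 2.3%.

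The zeros have a simple cause. When the shortest follow-up exceeds the median, nobody still on treatment is censored before the median, so moving those dates cannot affect it.

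**Step 4: the interim rule.** With 400 patients (80% of 500), a true median of 11.1 months and cut-off at the end of 18 or 30 months' accrual, suppose all stops up to the cut-off are in the database. The simulated medians are then:

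- cut-off censoring (the SAP rule): 11.15 / 11.13 months;
- last-visit censoring: 10.70 / 10.92 months.

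The SAP rule recovers the true value closely. Last-visit censoring is biased downward because it counts events after the last visit but discards event-free time over the same days.

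**The case against.** **The gap may be zero, and the rule has a workable reading.** The EOT visit may fall on the day of the last dose. The second rule can be read as meaning patients on drug until the study closes, censored at a closing visit where symptoms are assessed. This stands in part: 14 days is a ceiling. But progression found at that visit and recorded as the reason for stopping would be dated back to the last dose, so the gap still cannot contain an event. Nor do the documents say that removed patients are recorded as 'other'; the overlap of the two rules depends on that.

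**The effect is small and nothing is tested.** This also stands. It limits the weight of the point but does not settle which date applies.

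**Relevant rules may be hidden.** Some SAP text on efficacy data handling and further endpoints is not visible, so TTSP should not be called the only efficacy endpoint, and related date rules may exist. The visible censoring rule is nevertheless explicit.

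**A reader might infer that the interim rule is biased too.** The documents do not support that. At the interim the two rules cover different patients, those who stopped and those who did not. Because an event is a stop of afatinib, a patient confirmed on treatment at the cut-off is event-free to that date. Bias needs stops that are missing from the database. If every stop since the last 28-day visit were missing, the simulated median would rise by 2.3 to 10.0 days. No passage says data are extracted in that state, and Protocol 6.2.3 asks for the EOT visit as soon as the drug is discontinued.

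**Conclusion.** The point holds for the final analysis only. Censoring at the EOT visit adds up to 14 days per affected patient in which no event can be recorded, and the group it applies to is not properly defined. The direction is upward or nil and follows from the definitions alone. The size rests on the assumptions in step 3: 0 to about 9 or 10 days on the median and up to about 20 days on the 75th percentile. With 12 or more months of follow-up after accrual, the median moves by at most 1.2 days.

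The largest shifts need short follow-up, a large share still on treatment and every gap at its maximum, so it would be wrong to say that TTSP is materially inflated. The primary safety endpoint is unaffected. The correction is worth making because the rule is ambiguous whatever its size and costs little to repair.

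**What to change.** In the second censoring rule of SAP 7.5.2, for the final analysis, replace the EOT-visit date with the date of last administration of trial drug. Every patient without an event is then censored on the same basis as events, and it no longer matters which rule a sponsor-removed patient falls under.

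Keep cut-off-date censoring at the interim, and add that it applies to patients whose on-treatment status is confirmed at the cut-off. Do not substitute last-visit censoring.

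The cost is one changed phrase, one added condition and a line of programming. The date of last dose is already collected on the termination page. Confirming status at the interim cut-off needs some data-management effort. The downside for the sponsor is that the reported TTSP may be slightly less favourable.

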## **7.7 EXTENT OF EXPOSURE**

Total treatment time (days) will be calculated for each patient; total treatment time will include any dose interruptions or off-drug periods.

The definition of exposure is:

Treatment stop date – treatment start date + 1

In case of death due to any cause, the treatment stop date will be imputed as the earlier of (date of last administration of afatinib treatment, date of death) + 1 day

Standard descriptive summaries of these data will be provided for the treated set of patients.

Total treatment time (days) will be summarized by afatinib dose level (40 mg, 30 mg, 20 mg and total), and by number of therapy lines. The number of therapy lines for afatinib will be

derived as: the number of all previous therapy lines + 1. The number of all previous therapy lines that the patient received prior to the start of the treatment includes number of lines of all of the following:

- Systemic chemotherapies: count the number of previous chemotherapies obtained from the field “Line of therapy” on the previous chemotherapies eCRF page .
- Other anti-cancer therapies: count the number of anti-cancer therapies obtained from the field “Line of therapy” on the other anti-cancer therapies eCRF page. If there is a therapy with the same name and same start and end dates as a therapy present in Systemic chemotherapies eCRF page, then ignore this as it has already been counted earlier.

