In study 1200.32 (LUX-Lung 3) treatment with afatinib resulted in a significantly prolonged PFS as compared to treatment with chemotherapy by independent review (median 11.1 vs 6.9 months, HR 0.58; 0.43–0.78; $p=0.0004$). In patients with common EGFR mutations (Del19/L858R), the median PFS for afatinib treated patients was 13.6 months as compared to 6.9 months for patients receiving PC (HR=0.47; 0.34-0.65; $p<0.0001$). The ORR for patients treated with afatinib (56%) was significantly higher than that for patients treated with PC (23%) ($p<0.0001$). The prolonged PFS and higher ORR observed in patients treated with afatinib were accompanied by significant delays (as compared to patients treated with PC) in time to deterioration of the cancer-related symptoms of cough (HR=0.60, $p=0.0072$) and dyspnoea (HR=0.68, $p=0.0145$). The pre-specified number of events necessary to evaluate Overall Survival (OS) has not yet been reached.

In the afatinib arm, the highest CTCAE Grade of AEs was Grade 3 in 51.1%, Grade 4 in 3.9%, and Grade 5 in 5.7% of patients. In the chemotherapy arm, the highest CTCAE Grade of AEs was Grade 3 in 44.1%, Grade 4 in 9.9%, and Grade 5 in 2.7% of patients. The incidence of patients with AEs leading to dose reduction was 57.2% (afatinib) and 16.2% (chemotherapy). The incidence of AEs leading to treatment discontinuation was 14.0% (afatinib) and 15.3% (chemotherapy). Drug-related AEs leading to treatment discontinuation were experienced by 7.9% (afatinib) and 11.7% of patients (chemotherapy). SAEs were reported in 28.8% (afatinib) and 22.5% (chemotherapy) of patients, 14.4% of patients in each treatment arm experienced drug-related SAEs. The most frequent SAEs related to treatment with afatinib were diarrhoea (6.6%) and vomiting (3.5%). The most frequent SAEs related to chemotherapy were vomiting (2.7%) and fatigue (2.7%). There were 13 deaths (5.7%) reported due to on-treatment AEs in the afatinib arm, with 4 of them (sepsis, dyspnoea, acute respiratory distress syndrome, and death) considered related to afatinib by the investigator. Three deaths (2.7%) were reported due to on-treatment AEs in the chemotherapy group; none of them were considered related to chemotherapy by the investigator. [[U12-1199-01](#)]

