Patient Status	Document any information regarding the patient's status during the planned observation time (i.e., 28 days after the patient's last dose of medication). When applicable, every effort should be taken to collect and document information on date of death. Note: any AE which results in death is considered an SAE.	Any new anti-cancer medication (including date when the new anti-cancer medication is taken) that the patient has taken since EOT visit. Date when the patient completed the planned observation time. Date of death Patient's status

Proprietary confidential information.

© 2019 Boehringer Ingelheim International GmbH or one or more of its affiliated companies. All rights reserved.

This document may not - in full or in part - be passed on, reproduced, published or otherwise used without prior written permission.

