## **6. GENERAL ANALYSIS DEFINITIONS**

### **6.1 TREATMENT**

There is only one treatment in this study, which is afatinib. The starting dose for all patients is 40 mg with an option to reduce the dose to 30 mg or 20 mg based on individual tolerability. Unless otherwise stated, for all analyses, treated patients will be presented under the starting dose.

The following study periods based on key visit dates and actual start and stop dates of study treatment administration are defined:

- Screening: From day of informed consent to day prior to starting study treatment.

Special handling rule:

If informed consent date = date of first administration of active treatment in the trial, derive start of screening phase on the day of informed consent – 1 day.

- On-treatment: From day of first administration of study treatment to the day of last administration of study treatment.
- Residual effect period (REP): From day after last administration of study treatment to the 28th day after last administration of study treatment.
- Follow-up: After the residual effect period and up to the last per protocol contact.
- Post-study: After the last per protocol contact but entered in the database before database lock.

For safety summaries data recorded up to 28 days after last administration of study treatment will be considered as on-treatment (i.e. the actual on-treatment and REP periods defined above will be combined into one 'on-treatment' analysis period).

Safety data recorded after follow-up period will be listed as post-study events but not tabulated.

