## **6.6 HANDLING OF MISSING DATA AND OUTLIERS**

Missing or incomplete AE dates are imputed according to BI standards (see “Handling of missing and incomplete AE dates”).[\(1\)](#)

For efficacy data, the following rules will apply:

In addition, time since first diagnosis of NSCLC will be calculated from the date of diagnosis and the date of the start of the study treatment. As the date of diagnosis is likely to be partial in many cases, the following rules will be used

- If day is missing but month and year are present, impute to first day of the month.
- If only year is present, set to January 1st.

For partial treatment discontinuation date, the following logic is applied:

If month and year are known but day is missing, then use date of death if within the same month for a patient who died. Otherwise use last day of the month.

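### SAP 7.7 counts one treatment day too many for every patient with a recorded death, against the treatment period in SAP 6.1

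*SAP*

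**What the plan says.** SAP 7.7 (Extent of exposure) defines exposure as "Treatment stop date – treatment start date + 1", with interruptions and off-drug time included. It then gives a separate rule for patients who die of any cause: "the treatment stop date will be imputed as the earlier of (date of last administration of afatinib treatment, date of death) + 1 day". The results feed descriptive tables: "Total treatment time (days) will be summarized by afatinib dose level", in total, and by number of therapy lines.

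SAP 6.1 (Treatment) sets the study periods. On-treatment runs "From day of first administration of study treatment to the day of last administration of study treatment". The residual effect period runs "From day after last administration of study treatment to the" 28th day after that administration.

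Two other sections use the same dates without an extra day. SAP 7.5.2 derives time to symptomatic progression (TTSP) as date of last administration minus start date plus 1. SAP 6.6, for a discontinuation date with the day missing, says "then use date of death if within the same month for a patient who died".

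**The concern.** A duration from day s to day e, counting both ends, is e - s + 1. SAP 6.7 calls the first dosing day Day 1 and has no Day 0, so the one plus 1 in the exposure formula is all that an inclusive count needs. The death rule adds a second day by shifting the stop date before the formula is applied.

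Two patients with the same first and last dose would then have different total treatment times only because one has a recorded death. The rule has no time limit and is not restricted to missing stop dates. It therefore also reaches deaths after afatinib has stopped, such as those recorded at follow-up, where Protocol Table 6.2.4: 1 asks for the patient's status during the "planned observation time (i.e., 28 days after the" last dose.

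What is at stake is the accuracy and internal consistency of the exposure tables in a trial whose primary objective is safety. No test or endpoint depends on it.

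**Working it through.** The documents state no exposure figure, so there is none to reproduce. The check is date arithmetic.

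**Inputs**
- Exposure formula and stop-date rule for deaths: SAP 7.7.
- On-treatment and residual effect periods: SAP 6.1.
- Partial discontinuation date: SAP 6.6.
- TTSP formula: SAP 7.5.2.
- Planned size, about 500 patients: Protocol 3.3.
- Assumption: for a patient with no recorded death, the stop date is the date of last administration. SAP 7.7 does not say this, but SAP 6.1 and 7.5.2 use that end date.

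**Formulas**
- No recorded death: E = last - start + 1.
- Recorded death, SAP 7.7 as written: E = [min(last, death) + 1] - start + 1. The last dose cannot follow death, so with a known last-dose date E = last - start + 2.
- On-treatment length in SAP 6.1: last - start + 1.
- Difference for a recorded death: exactly 1 day.

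**Worked cases** (start = day 1, last dose = day 100)
1. No recorded death: 100 - 1 + 1 = 100.
2. Death on day 120: stop = min(100, 120) + 1 = 101, so E = 101 - 1 + 1 = 101. Day 101 is day 1 of the residual effect period.
3. Discontinuation day missing, death on day 100 in the same month: if the date set by SAP 6.6 (day 100) is carried into SAP 7.7, stop = min(100, 100) + 1 = 101, one day after death.
4. Patient who stops for progressive disease on day 100 and later dies: TTSP = 100 - 1 + 1 = 100, but exposure = 101.

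The difference stayed at 1 day for eight durations from 1 to 730 days, with death 0, 1, 20 or 100 days after the last dose. In relative terms it is 1/28 = 3.6% at 28 days, 1/100 = 1.0% at 100 days and 1/335 = 0.3% at 335 days.

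**Effect on the mean:** shift = (proportion with a recorded death) x 1 day.

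| Proportion who die | Source | Mean shift | Extra patient-days in 500 |
|---|---|---|---|
| 5.7% | Protocol 2.3, trial 1200.32 | 0.057 day | 28.5 |
| 5.9% | Protocol 2.3, trial 1200.34 | 0.059 day | 29.5 |
| 6% | assumed | 0.06 day | 30 |
| 12% | assumed | 0.12 day | 60 |
| 100% | ceiling | 1 day | 500 |

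The first two rows come from other trials and count only deaths due to on-treatment adverse events (for 1200.32: "There were 13 deaths (5.7%) reported due to on-treatment AEs in the afatinib arm"). They are not rates of death from any cause.

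**With the extra day removed:** E = min(last, death) - start + 1. Cases 2, 3 and 4 all give 100, and E equals the SAP 6.1 on-treatment length in every case tested.

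**The case against.** The best counter-argument is that the wording can be read in ways that do no harm. The extra day may only repeat the plus 1 of the exposure formula, or it may belong to the date of death alone. On the first reading no exposure is wrong. On the second nothing changes when the last-dose date is known. But the sentence defines the stop date rather than exposure, and the parenthesis closes after both dates, so the text supports neither. If repetition was meant, the phrase is redundant and the same deletion applies.

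It can also be said that the stop date is imputed, so the rule is for missing dates only, and the eCRF collects the date of the last dose. That is a plausible intention, but the rule is stated for death from any cause and has no such limit.

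Some of the case against does stand. The comparison with patients not recorded as dead rests on the stop-date assumption listed above. The link from SAP 6.6 to SAP 7.7 is inferred, so the stop date one day after death is a conditional example. SAP 6.1 allocates data to periods while SAP 7.7 measures a duration, so the inconsistency misallocates no data. And the practical effect is very small.

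**Conclusion.** The point holds. Read as written, SAP 7.7 overstates total treatment time by one day for each patient with a recorded death and counts the first residual effect day as treatment. This rests on last administration being the stop date for everyone else.

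The size is minor: about 0.06 day on the mean at around 6% deaths, 0.12 day at an assumed 12%, and never more than 1 day. Only the descriptive exposure summaries (total, by dose level, by number of therapy lines) are affected. The SAE and drug-related adverse event counts, the treatment-emergent window and TTSP are all defined from the last-dose date directly and do not change. It is a tidy-up worth making, and it would not alter any conclusion of the trial.

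**What to change.** In SAP 7.7, delete the added day from the rule for deaths, so that the treatment stop date is the earlier of the date of last administration and the date of death. Keep exposure as stop date minus start date plus 1 for all patients. In the same edit, it would help to state that the stop date is the date of last administration for patients who have stopped afatinib and have no recorded death, since the section leaves this unsaid.

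The cost is a small change of SAP text and one line of programming. No new data are needed.
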